9. Examine impact of the everolimus based regimen on cardiovascular health as measured by pulse wave velocity and augmentation index as derived from applanation tonometry. It is expected that the superior GFR, improved blood pressure and decreased sympathotonia expected with everolimus based tacrolimus minimization will improve indices of vascular stiffness and in turn, overall cardiovascular health.
10. An exploratory objective will examine the tissue expression (immunohistochemistry) TGF beta (marker of Epithelial to Mesenchymal transformation (EMT), a precursor of fibrosis and Bone Morphogenetic Protein-7 (BMP-7; Marker of anti-fibrotic events).

Population: Sixty adult renal transplant recipients that give informed consent and meet inclusion and exclusion criteria will be enrolled and randomized in this trial, 30 patients in each group. Patients will be screened, approached, and consented between 10 weeks and 16 weeks post-transplant and randomized at approximately 12 weeks post-transplant to either continue on standard immunosuppressant therapy (control arm) or transition from mycophenolate to everolimus, with a significant reduction in tacrolimus dose and goal trough concentrations. Patients that are screened and consented, but are not randomized to a group will be replaced, such that there will be 30 patients in each group. Once patients are randomized and placed in a study group, they will be followed per study protocol and the analysis will occur in an intent-to-treat methodology.

Inclusion criteria:

1. At least 18 years of age and able to give informed consent.
2. Received a first or repeat cadaveric (including ECD) or living donor renal transplant.
3. Patient has stable graft function, defined as no change of greater than 40% of baseline serum creatinine and no acute rejection during the past month.
4. Currently receiving tacrolimus, mycophenolate mofetil and prednisone as their immunosuppression regimen

Exclusion criteria:

1. Biopsy proven acute rejection episode that occurred within the past month.
2. Malignancy within the past 3 years, except for non-melanoma skin cancer.
3. Currently enrolled in an investigational drug trial.
4. Woman of child bearing potential not utilizing an effective form of birth control.
5. Patients with uncontrolled dyslipidemia, defined as serum fasting LDL >200 mg/dL or serum fasting triglycerides >500 mg/dL.

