6. Patients with a spot urine protein to creatinine ratio of > 800 mg of protein per gram of creatinine.
7. WBC < 2,000 cells/mm³
8. Platelets < 75,000 cells/mm³
9. Patients who have received an organ transplant other than a kidney.
10. Patients with a history of biopsy proven FSGS, MPGN, or PGN.

Number of centers & patients: Single-center study, enrolling 60 consecutive kidney transplant recipients that meet criteria, give informed consent, and are randomized at 12-weeks (10-16 week timeframe) to either treatment group or control group..

Investigational and reference therapy:

Patients will be randomized to the standard immunosuppression arm (control arm) or the investigational immunosuppression arm (investigational arm). Randomization will occur once written informed consent has been obtained, patient meets inclusion and exclusion criteria and is three months post-transplant.

- **Arm 1 (standard of therapy):** tacrolimus, mycophenolate and corticosteroids.
- **Arm 2 (investigational therapy):** reduced-exposure tacrolimus, conversion of mycophenolate to Zortress® (everolimus) at 3 month post-transplant and corticosteroids.

In both study groups, either basiliximab 20 mg IV will be administered on post-operative day (POD) 0 and 4, or rabbit anti-thymocyte globulin 1.5 mg/kg on POD 0, 1, 2, 4 and 5. Choice

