All renal allograft biopsies (both protocol based and for cause) will have core tissue immediately stabilized in RNAlater[®] to prevent mRNA degradation. These samples will be stored at -70° C until processing. Absolute levels of mRNA will be quantified using preamplification-enhanced real-time quantitative polymerase-chain reaction

(PCR) assays with the use of oligonucleotide primers and TaqMan probes. The specific mRNA that is quantified will be determined by study investigators at the time of analysis, as this is a rapidly changing field and new mRNA targets may be found while the study is recruiting. At this time, mRNA targets are proposed to include CD3 ϵ , perforin, granzyme B, proteinase inhibitor 9, CD103, IP-10, CXCR3, and transforming growth factor β 1 (TGF- β 1).

N. Urinary Proteomics

These analyses will be conducted using the algorithms developed by [name] and [name]. Urine samples will be stored at -80 degree C for proteomic analysis. Proteins will be denatured, alkylated and digested with trypsin. Each sample will be pre fractionated using offline reversed phase solid phase extraction. Solid phase extraction fractions will be analyzed using LC-MS/MS. Tandem mass spectrometry will be performed using an AB SCIEX (Framingham MA) Triple TOF 5600 mass spectrometer. The Scaffold unweighted spectral counts of identified proteins will be normalized to internal standard protein in each sample and the relative abundance of each protein will be reported in normalized spectral counts.

O. Pulse Wave Velocity and Augmentation Index

Measurements of pulse wave velocity and vascular stiffness will occur at prespecified time points as delineated in the Study Evaluation Schedule located in the Appendix at the end of this protocol (baseline, month 3 and month 12 post-transplant). The following procedure will be used to obtain each of these measurements: After participants have rested for at least 10 minutes in the supine position, arterial waveforms at the radial arm (not containing vascular access grafts or fistulas), carotid, or femoral artery pulses will be recorded by applanation tonometry.

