Assessments		Pre-Txp	Day Post-transplant							Week Post-Txp		Month Post-transplant			
Time Frame			1	2	3	4	5	6	7	2	4	3	4	6	12
RANDOMIZATION												X (10-16 week window)			
History and Physical ²		X								X	X	X	X	X	X
Vital Signs		X	X	X	X	X	X	X	X	X	X	X	X	X	X
Protocol Kidney Biopsy												X			X
Donor Specific Antibody Analysis												X			X
Pregnancy testing ⁷		X	X (anytime between day 1-7)											X	X
Serologies ¹		X													
Laboratory Assessment	CBC and Chem-7 ⁴	X	X	X	X	X	X	X	X	X	X	X	X	X	X
	Total cholesterol, HDL, LDL, triglycerides ³	X										X	X		X
	Spot Urine Protein/Creatinine Ratio											X	X		X
	Tacrolimus levels ⁵			X	X	X	X	X	X	X	X	X	X	X	X
	Everolimus levels											X	X	X	X
Clinical assessment ⁶		X	X	X	X					X	X	X	X	x	X
EKG		X													
Estimated GFR		X	X	X	X	X	X	X	X	X	X	X		x	X
Genomic, RNA and proteomic analysis ⁴												X			X
Applanation tonometry using pulse wave velocity and augmentation index		One Baseline Measurement										X			X

Foot notes:

- Includes testing for CMV, Epstein-Barr, hepatitis B & C and HIV for donor and recipients (from evaluation or within one year pre-transplant if the results were negative at pre-transplant evaluation)
- Within 48 hours prior to transplant
- Fasting for at least 8 hours
- Includes genetic SNP analysis, mRNA expression, and urinary proteomic analysis
- Tacrolimus concentrations will be measured daily during the first week post-transplant once tacrolimus is initiated
- Includes assessments of blood pressure, weight changes, arterial stiffness measurement, adverse events, study drug doses, allograft rejection, infection, need for dialysis, hospitalization, re-transplant status, and other immunosuppressant medications
- Includes pregnancy test for females of child-bearing potential

Key references:

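### The baseline tonometry recording is scheduled before the consent window opens, and no recording is named as the analysis reference

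*Combined protocol and SAP*

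**What the plan says.** Study Procedures and Definitions, section O, gives the tonometry times as "baseline, month 3 and month 12 post-transplant" and refers to the evaluation schedule. In that schedule the tonometry row opens with "One Baseline Measurement" in the pre-transplant position, followed by a mark at month 3 and a mark at month 12.

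The Population paragraph fixes when patients enter the study: "Patients will be screened, approached, and consented between 10 weeks and 16 weeks post-transplant". They are then "randomized at approximately 12 weeks post-transplant". The section on investigational and reference therapy confirms the order: "Randomization will occur once written informed consent has been obtained". The schedule enters randomisation only in the month-3 column, with the same 10 to 16 week window.

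A schedule footnote defines the content of the clinical assessment: "Includes assessments of blood pressure, weight changes, arterial stiffness measurement, adverse events, study drug doses". That row is marked at many more visits than the tonometry row.

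Arterial stiffness is objective 9, one of those labelled exploratory. The Statistical analysis section does not mention tonometry.

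**The concern.** A recording made before transplant cannot be a consented study procedure if patients are first approached ten or more weeks after transplant. Site staff have three options: skip it, obtain it under some arrangement that the protocol does not describe, or treat month 3 as the baseline on their own initiative. Different patients could end up with different reference values.

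The footnote adds a second ambiguity about when arterial stiffness is measured. With no reference named for analysis, the choice between the first recording and the month-3 recording could be made after the data are seen. At stake are the completeness, precision and pre-specification of the cardiovascular comparison.

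**Working it through.** The plan states no figure for the tonometry endpoint, so the check is mainly of timing.

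**1. Tonometry against consent.** The inputs are the tonometry row of the evaluation schedule and the consent window in the Population paragraph.

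| Item | Time |
|---|---|
| First tonometry entry, read as pre-transplant | week 0 or earlier |
| First tonometry entry, if the cell was merged as far as week 4 | week 4 at the latest |
| Earliest consent | week 10 |
| Randomisation | about week 12 (window 10–16) |
| Second tonometry entry | month 3, the randomisation column |
| Third tonometry entry | month 12 |

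Gap from first recording to earliest consent:
- pre-transplant reading: at least 10 − 0 = 10 weeks;
- merged-cell reading: at least 10 − 4 = 6 weeks.

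The recording precedes consent under both readings, so the conclusion does not depend on how the table was extracted.

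**2. Tonometry row against the clinical-assessment footnote.** The clinical-assessment row is marked at 10 visits: pre-transplant; days 1, 2 and 3; weeks 2 and 4; months 3, 4, 6 and 12. The tonometry row has 3 entries. If the first of these is pre-transplant, the footnote implies 10 − 3 = 7 further measurement visits (days 1, 2 and 3, weeks 2 and 4, months 4 and 6). Six of the 10 marked visits fall before week 10. The clinical-assessment description in section B of the procedures does not list arterial stiffness.

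**3. Which recording is the reference?** No section says. For eGFR, section A of the Safety Assessment Definitions equates baseline with randomisation. The Statistical analysis section measures fibrosis, eGFR, mRNA and proteomic change from month 3 to month 12. Everolimus starts at month 3. The month-3 tonometry value therefore fits the rest of the plan, but the documents do not say that it is taken before conversion.

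**4. Bias.** Let R be any value recorded before randomisation and Y the month-12 value. Randomisation gives E(R | everolimus) = E(R | control), so

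E(Y − R | everolimus) − E(Y − R | control) = E(Y | everolimus) − E(Y | control).

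This holds for a pre-transplant R as well as a month-3 R. Changes due to transplantation and to the common early therapy cancel between arms in expectation.

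**5. Precision.** Assume equal variance σ² at both times and correlation ρ between R and Y. Per-patient variances are:
- month-12 value alone: σ²;
- change from R: 2σ²(1 − ρ);
- month-12 value adjusted for R: σ²(1 − ρ²).

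Adjusted over change: (1 − ρ²) / [2(1 − ρ)] = (1 + ρ)/2, which is below 1 for every ρ below 1. Adjusted over unadjusted: 1 − ρ², which is at most 1. Adjustment is therefore never worse, apart from one degree of freedom, and gains more as ρ rises. The documents give no ρ. I assume that it is higher for a month-3 value than for a pre-transplant one, because the month-3 value is nearer in time and follows the transplant.

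**6. Primary endpoint.** SD = √[(41² + 71²)/2] = 57.97; difference = 64 − 13 = 51; SE = 57.97 × √(2/27) = 15.78. Normal-approximation power is Φ(51/15.78 − 1.96) = Φ(1.27) = 89.8%, or 88.7% with the noncentral t. The stated 89% reproduces, and the tonometry schedule has no part in it.

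**The case against.** The strongest reply is that a usable baseline already exists. Tonometry is scheduled in the randomisation column, eGFR already takes randomisation as baseline, and other outcomes run from month 3 to month 12. That stands. A reader might infer that the endpoint has no workable baseline, but the schedule does not support this. What is missing is a statement that the month-3 value is the reference and precedes conversion.

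A second reply is that listing baseline apart from month 3 proves nothing. The physical examination section also lists screening/randomisation alongside month 3, although randomisation is at month 3. This is fair as to the wording of section O. It does not explain the schedule, where the baseline entry sits in a different column from the month-3 mark.

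Third, the early recording might be usual care or covered by a separate consent. Consent pages are not in the file, so this cannot be excluded. However, the protocol assigns laboratory and pregnancy testing to routine follow-up and says nothing similar of tonometry, which it describes as a dedicated device procedure on participants.

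Fourth, the footnote may list what a clinical assessment can contain, not what is done each time. Some of its items, such as re-transplant status, cannot apply before transplant. That weakens the footnote as evidence of planned extra measurements, but it still conflicts with the tonometry row on its face.

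A reader might also infer that a pre-transplant reference would confound the treatment comparison with the transplant and the first three months of therapy. Step 4 shows that it would not.

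**Conclusion.** The schedule conflict is real: the baseline tonometry recording falls at least 6 weeks, and on the plain reading at least 10 weeks, before the earliest consent the protocol allows. As written, it cannot be collected prospectively as a consented study procedure. The clinical-assessment footnote does not match the tonometry row, and no recording is named as the analysis reference.

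The consequence is minor. It is confined to exploratory objective 9, and the primary endpoint and its power are untouched. A pre-transplant reference would lose precision and would be missing for an unknown share of patients. Its availability is settled before randomisation, so restricting the analysis to patients who have it would shrink the sample but not, in expectation, tilt the arms. It is tempting to say that all 60 patients would lack this recording. That is only an upper bound, reached if no tonometry is done outside the study before consent, and the documents do not settle that.

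The conclusion assumes that the protocol text is complete on consent timing and that the first table entry lies no later than week 4.

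**What to change.** 1. Reconcile the Population paragraph, section O and the evaluation schedule. Delete the recording before month 3, or keep it only as optional descriptive data where valid consent for it exists.
2. Remove arterial stiffness from the clinical-assessment footnote, so that the tonometry row alone sets the times.
3. Name the month-3 recording as the tonometry baseline, in line with eGFR, and state that it is taken after consent and before conversion to everolimus.
4. Add to the Statistical analysis section that month-12 pulse wave velocity and augmentation index will each be compared between arms by a linear model adjusted for the month-3 value. The plan's general rule for continuous variables is an unadjusted t-test or rank-sum test, and tonometry is not named there.

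This needs a text and schedule correction. It adds no visits or patients and removes one recording per patient if the early one is deleted. What is given up is a description of arterial stiffness before transplant, which objective 9 does not need. Keeping that description for everyone would mean seeking consent earlier, including from patients who may never be randomised.

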Applanation tonometry will be performed by placing a micromanometer-tipped probe against the skin surface over the artery of interest and obtaining pressure waveforms transmitted through the skin surface. Pressure waveforms will be recorded during an 8-second period using a high-fidelity SPC-301 micromanometer (Millar Instrument, Inc., Houston, TX, USA) interfaced with a computer employing SphygmoCor, version 9.0 software (AtCor Medical Pty. Ltd., West Ryde, New South Wales, Australia). To determine aortic BP, the pulse wave obtained from radial tonometer recordings will be calibrated by manual measurement (auscultation) of brachial BP taken immediately before the recordings. The radial pressure waveform will be converted into a central (aortic) waveform using a validated generalized transfer function (GTF) incorporated in SphygmoCor software. Central aortic systolic and diastolic BP will be derived from the aortic waveform and PPc will be calculated from the difference.

Safety Assessment Definitions:

A. Renal Function:

Renal function will be calculated by the eGFR using the 4-variable MDRD formula. Time points for calculations are delineated in the Study Evaluation Schedule located in the Appendix at the end of this protocol. The primary renal function assessments utilized for safety and efficacy analyses will be the eGFR at baseline (randomization) and at 12 months post-transplant.

B. Physical Examination:

A thorough physical assessment will be performed at screening/randomization and at months 3, 4, 6 and 12 post-transplant. Significant findings that are present prior to the start of the study will be included in the Relevant Medical History/Current Medical Conditions on the CRF. Significant findings made after the start of study medication which meet the definition of an AE will be recorded in the AE CRF.

C. Vital Signs:

Vital signs (radial pulse rate and blood pressure) will be recorded as indicated in the Study Evaluation Schedule located in the Appendix at the end of this protocol. Blood pressure and pulse rate will be assessed at the same arm each time of determination and after the subject has rested in the sitting position (may be supine if during hospitalization) for at least five minutes. Measurements will be recorded on the CRF.

D. Height and Weight:

Height and weight will be measured and recorded at screening and during follow-up visits when physical exams are performed. Results will be recorded on the CRF.

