E. Laboratory Evaluations:

All laboratory measurements will be performed at MUSC or referral centers that are routinely used as part of usual follow-up care. Specific information regarding the types and schedule of laboratory assessments can be found in the Study Evaluation Schedule located in the Appendix at the end of this protocol. Laboratory measurement results and date of collection will be recorded for the baseline and follow-up time points within the CRFs. Sample collection and analysis for the proteomics, genomics and gene expression analyses will be conducted as described in the above sections.

F. Pregnancy, contraception and assessment of fertility:

Pregnancy testing (serum) will be carried out for all females of child-bearing potential as described in the Appendix at the end of this protocol. Testing will be part of routine follow-up care and will be conducted pre-transplant, within 7 days of transplant and at months 6 and 12 post-transplant.

Females of reproductive potential taking mycophenolate must receive contraceptive counseling and use acceptable contraception as delineated below for the entire time while on mycophenolate and for 6 weeks after stopping mycophenolate, unless the patient chooses abstinence (she chooses to avoid heterosexual intercourse completely). Females of reproductive potential taking everolimus must receive contraceptive counseling and use acceptable contraception as delineated below for the entire time while on everolimus and for 8 weeks after stopping everolimus, unless the patient chooses abstinence (she chooses to avoid heterosexual intercourse completely).

Acceptable contraception methods for females of reproductive potential

Option 1 (monotherapy methods):

1. Intrauterine devices (IUDs)
2. Tubal sterilization
3. Patient's partner had a vasectomy

Option 2 (Choice one from category A AND one from category B):

1. Category A:
 - a. Estrogen and progesterone
 - i. Oral contraceptive pill
 - ii. Transdermal patch
 - iii. Vaginal ring
 - b. Progesterone only
 - i. Injection
 - ii. Implant
 - c. Barrier method
 - i. Diaphragm with spermicide
 - ii. Cervical cap with spermicide
 - iii. Contraceptive sponge
2. Category B:
 - a. Male condom
 - b. Female condom
 - c. Diaphragm with spermicide (for use with hormone therapy)
 - d. Cervical cap with spermicide (for use with hormone therapy)
 - e. Contraceptive sponge (for use with hormone therapy)

G. Choice of Safety measurements:

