The safety laboratory assessments (renal function, chemistry, hematology) selected are standard for the kidney transplant population. The blood levels of everolimus and tacrolimus are required for correct control of drug levels and dosing. The assessment of (serious) adverse events, including infections, graft loss, death, dialysis and details of certain viral infections (CMV and BKV) allow for proper assessments of safety related outcomes and side effects in this population.

Safety Monitoring:

A. Adverse Events:

An adverse event (AE) is any untoward medical occurrence (i.e., any unfavorable and unintended sign [including abnormal laboratory findings], symptom or disease) in a subject or clinical investigation subject after providing written informed consent for participation in the study. Therefore, an AE may or may not be temporally or causally associated with the use of a medicinal (investigational) product. The occurrence of adverse events should be sought by non-directive questioning of the subject at each visit during the study. Adverse events also may be detected when they are volunteered by the subject during or between visits or through physical examination, laboratory test, or other assessments. Abnormal laboratory values or test results constitute adverse events only if they fulfill at least one of the following criteria:

- they induce clinical signs or symptoms,
- they are considered clinically significant,
- they require therapy.

Clinically significant abnormal laboratory values or test results should be identified through a review of values outside of normal ranges/clinically notable ranges, significant changes from baseline or the previous visit, or values which are considered to be non-typical in subject with underlying disease. Investigators have the responsibility for managing the safety of individual subject and identifying adverse events. Adverse events should be recorded in the Adverse Events CRF with them accompanied by the following information:

- the severity grade: (mild: usually transient in nature and generally not interfering with normal activities, moderate: sufficiently discomforting to interfere with normal activities, severe: prevents normal activities)
- possibility of relationship to the study treatment (no/yes)
- its duration (start and end dates) or if the event is ongoing an outcome of not recovered or not resolved should be reported.

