- whether it constitutes a serious adverse event (SAE), if so report date should be provided
- action taken regarding study treatment
- whether other medication or therapies have been taken (concomitant medication/non-drug therapy)
- its outcome (not recovered/not resolved; recovered/resolved; recovering/resolving, recovered/resolved with sequelae; fatal; or unknown)

All adverse events should be treated appropriately by the PI or designee. Once an adverse event is detected, it should be followed until its resolution or until it is judged to be permanent, and assessment should be made at each visit (or more frequently, if necessary).

B. Serious Adverse Events:

An SAE is any adverse event which meets any one of the following criteria:

- is fatal or life-threatening
- results in persistent or significant disability/incapacity

- constitutes a congenital anomaly/birth defect
- leads to a hospitalization that is not related to a renal allograft biopsy, renal allograft rejection episode or infection

AEs and SAEs will be reported in accordance with the FDA Guidelines for Post-Marketing Reporting of Adverse Events 21 CRF 314.80 and 21 CRF 600.80

<http://www.fda.gov/medwatch/report/regs.htm>. Any serious adverse event or a non-serious adverse event that is related to the study and unexpected will be reported to the FDA, per reporting guidelines, as soon as possible, but no later than 15 working days. Any serious adverse event or a non-serious adverse event that is related to the study and unexpected will be reported to Novartis within 24 hours of occurrence. Further, all serious adverse events that are related to the study and are unexpected must be reported to The Medical University of South Carolina IRB within 10 days per The Medical University of South Carolina IRB Unanticipated Problems and Adverse Events Policy and Procedures reporting guidelines.

C. Pregnancy Reporting:

Any pregnancies occurring while the subject is on study treatment will be reported to Novartis within 24 hr of learning of its occurrence. The pregnancy should be followed up to determine outcome, including spontaneous or voluntary termination, details of the birth, and the presence or absence of any birth defects, congenital abnormalities, or maternal and/or newborn complications.

Statistical analysis:

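### Pregnancy is not an exclusion and no pregnancy test is scheduled at randomisation, so an unrecognised pregnancy could enter either arm, including a new start on everolimus

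*Combined protocol and SAP*

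**What the plan says.** **Testing.** Safety Assessment Definitions, section F, states that serum testing of women of child-bearing potential is part of routine follow-up care and "will be conducted pre-transplant, within 7 days of transplant and at months 6 and 12 post-transplant". The pregnancy row of the Evaluation schedule matches: one test before transplant, one at any time in days 1-7, and two later ones. The month-3 column, which holds randomisation with its 10-16 week window, has none.

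**Eligibility.** There are ten exclusion criteria. The only one that bears on this is item 4: "Woman of child bearing potential not utilizing an effective form of birth control". Inclusion criterion 4 requires that the patient be "Currently receiving tacrolimus, mycophenolate mofetil and prednisone as their immunosuppression regimen". Under Investigational and reference therapy, the conditions for randomisation are consent, eligibility and time since transplant. A negative pregnancy test is not among them.

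**Timing of entry.** Under Population, patients are "consented between 10 weeks and 16 weeks post-transplant and randomized at approximately 12 weeks post-transplant". The investigational arm begins everolimus at month 3.

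**Safeguards.** Section F says "Females of reproductive potential taking mycophenolate must receive contraceptive counseling and use acceptable contraception" for as long as they take it and for 6 weeks afterwards. It sets the same duty for everolimus, with 8 weeks afterwards. Under Physical Examination, "A thorough physical assessment will be performed at screening/randomization and at months 3, 4, 6 and 12 post-transplant". Under Adverse Events, "The occurrence of adverse events should be sought by non-directive questioning of the subject at each visit during the study". Under Pregnancy Reporting, "Any pregnancies occurring while the subject is on study treatment will be reported to Novartis within 24 hr" of its being learned of.

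**The concern.** The protocol treats drug exposure in pregnancy as something to prevent and to track. It requires contraception on both mycophenolate and everolimus, rapid reporting and follow-up of any pregnancy on study treatment, and it lists a congenital anomaly or birth defect as a serious adverse event. Its chosen detection tool is a serum test. That tool is absent at the one visit where the trial itself assigns a new drug.

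Both early tests are timed to the transplant and precede consent, so no protocol test establishes pregnancy status at entry in either arm. Item 4 of the exclusions asks whether a woman uses contraception, not whether she is pregnant; a woman whose contraception has failed without her knowing satisfies it.

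What is at stake is mainly participant safety: an unrecognised pregnancy could continue on mycophenolate or be newly exposed to everolimus, and no protocol test would find it until month 6. There is a smaller cost to the analysis. A patient who consents but is not randomised is replaced, whereas a randomised patient stays in the intent-to-treat population even if taken off the drug. A pregnancy found before randomisation therefore costs no analysed patient. One found later remains in its arm and could cost a 12-month biopsy.

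**Working it through.** The plan gives no figure on this point to reproduce. The check is a reading of the eligibility list against the test schedule, followed by calendar arithmetic.

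**Step 1: is the missing test real?** Section F and the Evaluation schedule are separate statements of the same plan. The table's columns are partly flattened in the text available, but the prose names months 6 and 12 for the later tests, and the table's two later marks fit that. Neither source has a test at month 3, so the gap does not come from how the table was read.

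**Step 2: inputs.**
- Last test before entry: days 1-7 (Evaluation schedule).
- Randomisation: weeks 10-16, days 70-112; planned week 12, day 84 (Population; Evaluation schedule).
- Next test: month 6 (section F), taken here as week 26, day 182.

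**Step 3: age of the last test at randomisation** (randomisation day minus test day).

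| Randomised at | Tested on day 7 | Tested on day 1 |
|---|---|---|
| Week 10 | 70 − 7 = 63 days (9.0 weeks) | 70 − 1 = 69 days (9.9 weeks) |
| Week 12 | 84 − 7 = 77 days (11.0 weeks) | 84 − 1 = 83 days (11.9 weeks) |
| Week 16 | 112 − 7 = 105 days (15.0 weeks) | 112 − 1 = 111 days (15.9 weeks) |

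**Step 4: wait from randomisation to the next test.**
- From week 10: 26 − 10 = 16 weeks.
- From week 12: 26 − 12 = 14 weeks.
- From week 16: 26 − 16 = 10 weeks.

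**Step 5: interval between the two protocol tests.** It runs from 182 − 7 = 175 days (25.0 weeks) to 182 − 1 = 181 days (25.9 weeks), and it contains the whole randomisation window. A pregnancy that begins after the first post-transplant week can therefore pass through entry without meeting a protocol test.

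**Step 6: how many women would lack an entry test?** The documents do not say. Assuming 10-30% of the 60 randomised are women of child-bearing potential, the count is 0.10 × 60 = 6 to 0.30 × 60 = 18. In the everolimus arm alone it is 0.10 × 30 = 3 to 0.30 × 30 = 9.

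**Step 7: effect on the design.** None. Sample size, alpha and power do not depend on this point. The only link is attrition: the power statement allows 30 − 27 = 3 patients per arm without paired biopsies, and a pregnancy found after randomisation could use one of them.

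**The case against.** The strongest reply is that the door is narrower than the heading suggests. Every candidate is already on mycophenolate, so the contraception duty applies before entry, and exclusion 4 bars women who are not using effective birth control. In practice that would stop most known pregnancies. An unrecognised pregnancy at entry then requires required contraception to have failed or not been followed. Patients also have a physical assessment at entry, another at month 4, and adverse-event questioning at every visit. Section F places testing within routine follow-up care, so a clinician might order a test near month 3 anyway.

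This stands as a reason to think the risk is small. It does not close the gap. Contraception rules do not detect a failure, and the protocol does not rely on them alone, since it tests again at months 6 and 12. The visits and the non-directive questioning are not pregnancy tests. Nothing requires a test around month 3 or makes a positive result exclusionary.

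A second objection is that randomisation to control creates no new exposure, because mycophenolate simply continues. That is correct: the only new drug is everolimus, planned for 30 of the 60. It is still true that pregnancy status is unverified at entry in both arms, and that continued mycophenolate is an exposure the protocol seeks to avoid.

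A third is that 6-18 is not a count of women at risk. That is also right. It is the number who would enter without a test, under an assumed share.

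**Conclusion.** The concern holds. Pregnancy is not an exclusion, and no protocol test falls in the window when patients are randomised and everolimus starts. The latest test is about 9-16 weeks old at that point and the next is about 10-16 weeks away, although a visit or a clinically indicated test could reveal a pregnancy sooner. The missing test and exclusion are certain from the text; the timing figures rest only on the stated windows and on taking month 6 as week 26.

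The chance that an unrecognised pregnancy is actually randomised cannot be estimated from these documents and, given the safeguards, is probably low. This is a participant-safety gap that should be closed because the possible harm is serious and the remedy is cheap. It does not threaten the primary analysis.

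**What to change.** 1. Add an exclusion criterion: pregnancy, shown by a positive serum test at screening or randomisation.
2. Add a serum pregnancy test for women of child-bearing potential to the month-3 column of the Evaluation schedule and to section F. Apply it in both arms, with the result available before randomisation and before the first everolimus dose.
3. As a minor clarification only, have exclusion 4 refer to the section F list of acceptable contraception, including abstinence.

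**Cost.** One assay per woman of child-bearing potential, on blood already drawn at month 3 for the CBC and Chem-7: about 6-18 assays among the 60 randomised under the 10-30% assumption. There is a short wait for the result, which fits within the 16 − 10 = 6-week randomisation window. No extra visit, staff or invasive procedure is needed.
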